2.6.4.2 Participant ADA status

Any IG sample collected after 150 days of the last dose of sabatolimab will not be used for summaries or derivations and will only be included in the listing.

Participant ADA status is defined as follows:

- Treatment-induced ADA-positive participant: participant with ADA-negative sample at baseline and at least one treatment-induced ADA-positive sample.
- Treatment-boosted ADA-positive participant: participant with ADA-positive sample at baseline and at least one treatment-boosted ADA-positive sample.
- Treatment-unaffected ADA-positive participant: participant with ADA-positive sample at baseline, no treatment-boosted ADA-positive samples, and at least one treatment-unaffected ADA-positive sample.
- Treatment-reduced ADA-positive participant: participant with ADA-positive sample at baseline and at least one post baseline determinant sample, all of which are ADA-negative samples.

- ADA-negative participant: participant with ADA-negative sample at baseline and at least one post baseline determinant sample, all of which are ADA-negative samples.
- Inconclusive participant: participant who does not qualify as treatment-induced ADA-positive, treatment-boosted ADA-positive, treatment-unaffected ADA-positive, treatment-reduced ADA-positive, or ADA-negative.

Listings will be provided of participant ADA status.

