Women of childbearing potential must be informed that taking the study treatment may involve unknown risks to the fetus if pregnancy were to occur during the study and agree that in order to participate in the study they must adhere to the contraception requirements for the duration of the study. If there is any question that the participant will not reliably comply, they should not be entered in the study.

Male participants, including vasectomized men, in the study, must agree not to father a child and to use a condom during intercourse, to prevent delivery of the drug via seminal fluid during the study, and for the period of 3 months after the last dose of azacitidine.

Prior to starting treatment, male participants are advised to seek consultation on sperm storage and female participants of childbearing potential should seek consultation regarding oocyte cryopreservation.

A copy of the approved version of all consent forms must be provided to Novartis/sponsor after IRB/IEC approval.

8 Visit schedule and assessments

Assessment schedule (Table 8-1) lists all of the assessments when they are performed. All data obtained from these assessments must be supported in the participant's source documentation.

Each treatment cycle is 28 days. Screening evaluations should be performed within \leq 28 days of Cycle 1 Day 1 (except for the pregnancy test which has to be performed within 72 hours before the first dose).

During the course of the study visits, test and/or procedures should occur on schedule whenever possible. A visit window of +/- 3 days is allowed for study procedures (including treatment administration). If sabatolimab administration on Day 8 is delayed within a cycle due to toxicities, visit assessments for Day 8 should be shifted accordingly or occur on Day 22, in case of no administration. See Section 6.1 for details on study treatment.

A window of +/-7 days from the planned visit date is allowed for BMA procedures. During the post-treatment and survival follow-up phases, a visit window of +/-14 days is allowed.

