Note: If a treatment cycle is delayed at any time during the study, all study visits and safety and efficacy assessments should continue according to the appropriate number of calendar days measured from Day 1 of the previous cycle, or more often if clinically indicated. When treatment is resumed, the first day of azacitidine and venetoclax administration will be considered as D1 of the new treatment cycle and visit schedule will be shifted accordingly.

On PK collection days the windows are provided in Section 8.5.2. Participants who discontinue the study treatment for any reason should be scheduled for an end of treatment (EOT) visit within 14 days from the decision to permanently discontinue study treatment, at which time all of the assessments listed for the EOT visit will be performed.

For efficacy follow-up and survival information, please refer to Section 8.3.1 and Section 9.1.

Novartis	
Amended Protocol Version 02 (Clean)	

Confidential

Table 8-1Assessment Schedule

Period	Screening	Treatment																		
Cycle			Сус	cle 1			Сус	le 2		(Cycle :	3		Cycle 4	4		Cycle #	5	Cycle 6	
Visit Name	Screening (- 28 to -1)	D1	D8	D22	D28	D1	D8	D22	D28	D1	D8	D28	D1	D8	D28	D1	D8	D28	D1	D8
Days	-28 to -1	D1	D8	D22	D28	D1	D8	D22	D28	D1	D8	D28	D1	D8	D28	D1	D8	D28	D1	D8
Informed consent	Х																			
IRT Registration	Х	Х																		
Demography	Х																			
Inclusion / Exclusion criteria	х																			
Medical history/current medical conditions	х																			
Disease History ¹	Х																			
Prior antineoplastic therapies	х																			
Prior/concomitant medications, surgery and medical procedures (including blood transfusions requirement) ²	х																			
Adverse Events	Х									С	ontinuo	us								
Physical Examination	S	S	S	S		S	S	S		S	S		S	S		S	S		S	S
Vital Signs	Х	Х	Х	Х		Х	Х	Х		Х	Х		Х	Х		Х	Х		Х	Х
Body Height	Х																			
BSA (use height from screening)		х				х				х			х			х			х	
Body Weight	X	Х				Х				Х			Х			Х			Х	
ECOG PS	Х	Х				Х				Х			Х			Х			Х	
Hematology	Х	Х	Х	Х		Х	Х	Х		Х	Х		Х	Х		Х	Х		Х	Х

Amended Protocol Version 02 (Clean)

Novartis

Page **69** of **143** Protocol No. CMBG453B12203

Period	Screening	Treatment																		
Cycle			Сус	le 1			Сус	le 2		(Cycle 3	3	(Cycle 4	ŀ	(Cycle 5	5	Cycle 6	
Visit Name	Screening (- 28 to -1)	D1	D8	D22	D28	D1	D8	D22	D28	D1	D8	D28	D1	D8	D28	D1	D8	D28	D1	D8
Days	-28 to -1	D1	D8	D22	D28	D1	D8	D22	D28	D1	D8	D28	D1	D8	D28	D1	D8	D28	D1	D8

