9.1.1.1 Safety follow-up

All participants must be followed for safety for 150 days after the last dose of sabatolimab or 30 days after the last dose of azacitidine or venetoclax whichever is longer.

After the 30-Day on-site safety follow-up visit, participants will be followed via telephone call (or on-site visit if participant happens to be visiting the site) at 90 and 150 days after the last dose of sabatolimab. All safety assessments should be completed as per Table 8-1. However, if the participant begins new antineoplastic medication before the end of the safety follow-up period, the collection of new SAEs and AEs unrelated to study medication will stop and thereafter only suspected AEs and suspected SAEs will continue to be collected up to the end of the safety follow-up period. For female participants of childbearing potential, a pregnancy test will be performed at the timepoints listed in Table 8-1.

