2.6.1.3 Handling of missing values/censoring/discontinuations for PFS, LFS and EFS

For participants without PFS/EFS/LFS events, PFS/LFS/EFS are censored at the last adequate assessment (response assessment for PFS/EFS, bone marrow/hematology assessment for LFS).

This is the last response/bone marrow/hematology assessment conducted that is not considered as unknown.

An event occurring after two or more consecutive missing response assessments (not done or unknown) is censored in the analysis at the last adequate response assessment before the event date and reason for censoring then summarized as 'Event documented after two or more missing response assessments'.

An exact rule to determine whether there are two missing assessments is therefore needed. This rule will be based on the distance between the last adequate response assessment date and the event date. If the distance is larger than threshold D_2 then the analysis will assume that there are two missing assessments. This threshold D_2 is defined as two times the protocol specified interval between the response assessments plus the allowed window around the assessments. The protocol defines that response assessment has to be done at least at the time of bone marrow assessments that are to be done:

- Pre-dose on C3D1, then
- From C7D1, bone marrow assessments will be performed every 3 cycles (12 weeks) until C13D1 (C7D1, C10D1, C13D1), then
- Every 6 cycles (24 weeks) until C25D1 (C19D1 and C25D1) and thereafter every 12 cycles (48 week, visit: C37D1, C49D1 etc.) and as clinically indicated during the treatment period).
- At least every 12 months during follow-up for efficacy

As per the protocol, a window of +/-1 week from the planned visit date is allowed for BMA procedures. During the post-treatment and survival follow-up phases, a visit window of +/-2 weeks is allowed.

The censoring reason will be summarized as:

- 1. Ongoing without event
- 2. New anti-cancer therapy
- 3. Withdrew consent
- 4. Lost to follow-up
- 5. Event documented after two or more missing response assessments
- 6. Discontinuation due to participant/physician/guardian's decision

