2.6.4 Immunogenicity

2.6.4.1 Sample ADA Status

Each IG sample is assessed in a three-tiered anti-drug anti-body (ADA) testing approach. All IG samples are analyzed in the initial screening assay (first tier). Samples testing negative in the screening assay are not subject to a confirmatory assay. Samples testing positive in the screening assay are then subjected to the confirmatory assay to demonstrate that ADA are specific for the therapeutic protein product (second tier). The titer of confirmatory positive samples will be subsequently determined in the titration assay (third tier). Samples identified as positive in the confirmatory assay are considered ADA positive. Samples can test negative in either the screening or confirmatory assay but for analysis purposes they are not differentiated. The following properties of each sample will be provided in the source data:

- Result of the assay according to a pre-specified confirmatory cut point: ADA positive (yes) or ADA negative (no)
- Titer (for positive samples): numerical representation of the magnitude of ADA response.
- When titer values are below the titer cut point with minimal required dilution (MRD) and the result is reported as 'Titer value 50 (MRD)', it is interpreted as a POSTIVE sample with titer equal to 50. Drug tolerance level: highest drug concentration that does not interfere with the ADA detection method

• Fold titer change (i.e. x-fold): threshold for determining treatment boosted

Determinant samples are defined as samples which are not unevaluable (where unevaluable = sample where assay is not available).

The following definitions apply only to determinant samples:

- ADA-negative sample: Determinant sample where the assay is ADA negative and MBG453 PK concentration at the time of IG sample collection is less than the drug tolerance level.
- ADA-positive sample: Determinant sample where the assay is ADA positive.
- ADA-inconclusive sample: Sample where assay is the ADA is negative and MBG453 PK concentration at the time of the IG sample collection is greater than or equal to the drug tolerance level or missing

The following definitions apply only to post-baseline ADA-positive samples with a corresponding determinant baseline sample. To be classified as treatment-boosted or treatment-unaffected, both the post-baseline and baseline titer must be non-missing:

- treatment-induced ADA-positive sample: ADA-positive sample post-baseline with ADAnegative sample at baseline.

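### The SAP's 150-day cut for immunogenicity samples falls on the nominal day of the scheduled 150-day sample, so one taken late but inside its visit window does not count towards participant ADA status

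*SAP*

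**What the plan says.** SAP 2.6.4.2 (Participant ADA status) sets an upper time limit on IG samples: "Any IG sample collected after 150 days of the last dose of sabatolimab will not be used for summaries or derivations". Later samples are kept, but for display only: they "will not be used for summaries or derivations and will only be included in the listing". No visit-window allowance and no reason for the limit are given.

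The protocol plans an IG sample at that time point. Table 8-1 and Table 8-9 list one at the 150-day safety follow-up, and Protocol 9.1.1.1 places the follow-up contacts "at 90 and 150 days after the last dose of sabatolimab". The contact is by telephone unless the participant happens to be at the site. A footnote to Table 8-9 leaves the sample to the investigator's discretion.

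Protocol Section 8 gives two windows that might govern this visit. One is a general allowance of 3 days either side for study procedures. The other reads: "During the post-treatment and survival follow-up phases, a visit window of +/-14 days is allowed". The SAP repeats the wider one in 2.6.1.3 ("During the post-treatment and survival follow-up phases, a visit window of +/-2 weeks is allowed"), but only to define missing assessments for PFS, LFS and EFS.

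**The concern.** The limit and the scheduled visit day are the same number, counted from the same dose. A rule meant to exclude samples beyond the follow-up period therefore also excludes the last scheduled sample whenever the visit is even one day late, although the protocol treats that visit as on time.

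What is at stake is the classification of individual participants. Someone who is ADA-negative at baseline and whose only positive sample is a late, in-window 150-day draw would be reported as ADA-negative or inconclusive instead of treatment-induced positive. The abbreviated CSR will still report immunogenicity (SAP 1.2), in a planned population of about 18, so one such participant would visibly change the reported percentage.

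**Working it through.** The plan states no figure on this point, so there is none to reproduce. The check sets the rule against the schedule and counts days.

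**Inputs**
- Last day on which an IG sample counts: Day 150 after the last sabatolimab dose (SAP 2.6.4.2).
- Nominal day of the scheduled follow-up sample: Day 150 after the last sabatolimab dose (Protocol 9.1.1.1, Tables 8-1 and 8-9).
- Candidate window half-widths w: 14 days or 3 days (Protocol Section 8).
- Planned participants: 6 in cohort 1, 12 in cohort 2, 18 in total (SAP 1.1). The expansion was not opened (SAP 1).

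**Which window applies.** The documents do not settle this. The wider window refers to the post-treatment and survival follow-up phases, but the protocol has separate headings for safety follow-up (9.1.1.1) and post-treatment follow-up (9.1.1.2), and the 150-day contact is under the former. In favour of the wider window, SAP 2.6.2 starts the post-treatment period on day 31 after the last administration of study treatment. Section 8 also says "On PK collection days the windows are provided in Section 8.5.2", but Table 8-9 there sets no day limit for the 150-day sample. Both windows are therefore carried through.

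**Days inside the window but past the cut.** The window has 2w + 1 days, of which w fall after Day 150.
- w = 14: Days 136 to 164, 2 × 14 + 1 = 29 days. Days 151 to 164 are past the cut: 14/29 = 48.3%.
- w = 3: Days 147 to 153, 2 × 3 + 1 = 7 days. Days 151 to 153 are past the cut: 3/7 = 42.9%.

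These are shares of allowed days, not of samples.

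**Direction of the effect.** SAP 2.6.4.2 requires at least one qualifying positive sample for treatment-induced status, and likewise for treatment-boosted status. Removing a post-baseline sample cannot create a qualifying positive, so the count in either category can only fall or stay the same.

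**Size of one reclassification**, with all planned participants in the denominator: 1/6 = 16.7 percentage points in cohort 1, 1/12 = 8.3 in cohort 2, 1/18 = 5.6 overall. Each would be larger if fewer participants have usable samples.

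**Consistency with the rest of the SAP.** Other timing rules include an allowance. The missing-assessment threshold in 2.6.1.3 adds the permitted window, and 2.6.3.1 accepts sabatolimab pre-dose samples within 3 days of the dosing interval. The IG limit has none.

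**The case against.** The strongest defence is that 150 days is deliberate. It is the end of safety follow-up, and SAP 2.6.2 defines an overall safety period ending on that day. Some upper limit is also needed, because Table 8-9 asks for an unscheduled IG sample at confirmed progression after an end of treatment for other reasons, which may come much later. This stands as an argument for having a limit. It does not explain why a scheduled sample should count on Day 150 and not on Day 151.

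Second, the stated endpoint is ADA incidence on treatment, and the on-treatment period ends 30 days after the last study treatment. A sample after Day 150 would normally lie well outside it. That is correct, but SAP 2.6.4.2 already uses follow-up samples up to Day 150, so it has itself gone beyond that period, and the inconsistency at the visit day remains.

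Three stronger readings are tempting, and the documents do not support them.
- A reader might infer that late samples are lost. They are not: they stay in the listing, where a positive result and its titer can be seen.
- A reader might infer that 40 to 50% of 150-day samples drop out. That would need visits spread evenly over the window, which nothing in the documents shows, and an optional, on-site sample may yield very few draws or none.
- A reader might infer a material downward bias, because the 150-day draw is furthest from dosing and so the likeliest to reveal ADA masked by drug. The drug tolerance level is not given, so the extent of masking is unknown. Assay-negative samples with a drug concentration "greater than or equal to the drug tolerance level or missing" are classed as inconclusive, so masking is not silently counted as negative. Samples at end of treatment and at 30 days are normally retained.

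**Conclusion.** The point holds as a minor inconsistency between the SAP cut and the protocol schedule. Under either window, a scheduled 150-day IG sample taken late but on time by protocol is left out of participant ADA status. The direction is known: the number of treatment-induced or treatment-boosted participants can only be lowered or left unchanged. The size is not known and is probably small, since it depends on how many optional on-site samples were drawn, how many of those fell after Day 150, and whether any was a participant's only qualifying positive. The 48% and 43% describe the window alone. The endpoint is secondary and descriptive; no primary endpoint, decision rule or sample size is affected.

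**What to change.** Amend SAP 2.6.4.2 to say that the nominal 150-day follow-up IG sample is used in participant ADA status and the related summaries when it is collected within its protocol visit window. State which window applies to safety follow-up visits: the upper limit is 150 + 14 = Day 164 under the post-treatment window, or 150 + 3 = Day 153 under the general one. Keep the 150-day cut for other, unscheduled later samples. If the hard cut at Day 150 is intended for the scheduled sample too, give the reason.

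The cost is a sentence or two in the SAP and a small change to the ADA program, with no new samples. The downside is that a few samples used in the summaries would fall just outside the 150-day overall safety period; a footnote can say so.

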2.6.5 Patient-Reported outcome: MDS symptoms and fatigue (Part II only)

Not applicable.

2.8 Interim analysis

No formal interim analysis is planned for this trial. However, two safety review meetings during the safety run-in part and a periodic safety review by the Steering Committee will occur approximately every 6 months in the expansion cohort.

In the Safety run-in (Part 1), the first safety review meeting will be conducted after participants included in the first cohort (N=6 with at least 3 evaluable participants treated with sabatolimab at the 400 mg Q4W) have completed 2 cycles of treatment. If the 400 mg Q4W dose of sabatolimab is considered to be safe in combination with venetoclax and azacitidine guided by the Bayesian analysis based on the incidence of dose limiting toxicity (DLT) data as well as all available safety, clinical pharmacology and tolerability data, a second cohort with 12 participants will be opened (sabatolimab at 800 mg Q4W). Otherwise the study will be stopped.

After completion of 2 cycles of treatment with at least 9 evaluable participants, the second safety review meeting will take place. The decision will be made based on DLT observation and the Bayesian model to open the Expansion (Part 2) (or not) at this dose level (sabatolimab at 800 mg Q4W) in combination with venetoclax and azacitidine. If sabatolimab 800 mg Q4W is considered to be safe, then Expansion (Part 2) will be opened at the same dose level (800 mg Q4W). Otherwise, the study will be stopped.

For each cohort (sabatolimab 400 mg and 800 mg Q4W) of the safety run-in part, the following information (summaries and/or listings) will be provided:

- Number (%) of participants treated and included in the analysis sets
- Basic demographic and background data
- Disease characteristics and medical history
- Concomitant medications
- Patient disposition
- Protocol deviations
- Duration of exposure to study treatment, Dose intensity and relative dose intensity, Number (%) of participants with any dose changes (incl. reductions, interruptions, or permanent discontinuations) and the reasons
- DLTs, AEs, treatment related AEs, SAEs, on-treatment deaths reported during the DLT evaluation period, as well as DLTs, AEs, treatment related AEs, SAEs, on-treatment deaths reported up to the data cut-off date
- Posterior distribution for the risk of DLT for new participants at the dose level tested (see Section 2.5.2.1)
- Laboratory data and vital signs abnormalities
- Blast counts from bone marrow and investigator's response assessment

Due to the recruitment halt, safety review meetings after the safety run-in part will not be conducted.

2.9 Sample size calculation

2.9.1 Safety run-in (Part 1)

No formal statistical power calculations to determine sample size were performed for this part of the study. However, the operating characteristics are reasonable based on the sample size for this part of the study. In case the starting dose (sabatolimab 400 mg Q4W (N=6)) with the fixed dose combination of azacitidine plus venetoclax is confirmed to be safe and tolerated for at least 3 evaluable participants, another cohort will be opened at 800 mg of sabatolimab Q4W (N=12) with fixed dose of venetoclax plus azacitidine with at least 9 evaluable participants. Otherwise, the study will be stopped.

In total, the Safety run-in (Part 1) is expected to enroll approximately 18 participants (6 participants for cohort 1 (sabatolimab (400 mg Q4W) and 12 participants for cohort 2 (800 mg (Q4W)) in order to have at least 12 evaluable participants (3 evaluable participants in cohort 1 and 9 evaluable participants in cohort 2).

2.9.2 Cohort 2 of Safety run-in (Part 1) and Expansion (Part 2) (CR primary analysis)

The sample size calculation is based on the Complete Remission (CR) rate (primary efficacy endpoint) for participants treated with sabatolimab 800 mg Q4W from Safety run-in (Part 1) and Expansion (Part 2).

Based on available data (Wei et al 2019), the CR rate with the combination azacitidine and venetoclax is expected to be around 39%. The first criteria to declare the trial successful is to test if the CR rate with sabatolimab in combination with azacitidine and venetoclax is at least 50% (statistical significance).

The Bayesian formulation of this dual criterion design can be expressed as below:

- Bayesian statistical significance: probability for a positive treatment effect (i.e. CR rate > 39% | data) ≥ 0.975.
- Clinical relevance: posterior median of CR rate \geq 50%.

With the two criteria stated above the minimally required sample (n_{min}) size is 67 and the sample size was set to 70 including participants from cohort 2 of the Safety run-in (Part 1) and the Expansion (Part 2). Thus, the total sample size is comprised of 76 participants (including the 6 participants treated at 400 mg Q4W in cohort 1 of the Safety run-in (Part 1). For 70 participants (included for the primary efficacy analysis), the table below shows data scenarios (number of participants achieving complete remission) with respective inferential results and decisions.

The minimum number of participants with CR to declare this trial successful (both statistical significance and clinical relevance met) is 36 out of 70 participants (51.4%).

Based on simulations (Table 2-5), a total of 36 responders out of 70 participants is required for trial success, with estimates of 51.4% for the posterior median CR rate and 98.3% for the posterior probability for a positive effect (CR > 39%). If the number of participants with CR is less than 36, both criteria are not met (NO-GO).

True CR rate	Posterior median CR	Posterior probability for a positive effect (CR>39%)	Decision for trial success
30/70 (42.9%)	43.0%	0.754	Failed
31/70 (44.3%)	44.4%	0.823	Failed
32/70 (45.7%)	45.8%	0.879	Failed
33/70 (47.1%)	47.2%	0.920	Failed
34/70 (48.6%)	48.6%	0.950	Failed
35/70 (50.0%)	50.0%	0.970	Failed
36/70 (51.4%)	51.4%	0.983	Successful

Table 2-5Data scenarios, inferential results and decisions (n=70)

A non-informative Beta (1,1) prior with mean 50% has been used in these calculations.

Operating characteristics for various true CR rates are presented in the table below. The type-I error under the null value (CR rate = 38.6%) is 2.0% and power is 80% assuming a true CR of 55.7 %.

Table 2-6Operating characteristics for true CR rate (n=70)

True CR rate	Probability of success (Go)	Probability of futility (No Go)
27/70 (38.6%)*	0.020	0.980
28/70 (40.0%)	0.035	0.965
29/70 (41.4%)	0.056	0.944
30/70(42.9%)	0.094	0.906
31/70 (44.3%)	0.140	0.860
32/70 (45.7%)	0.204	0.796
33/70 (47.1%)	0.272	0.728
34/70 (48.6%)	0.355	0.645
35/70 (50%)	0.452	0.548
36/70 (51.4%)	0.546	0.454
37/70 (52.9%)	0.644	0.356
38/70 (54.3%)	0.721	0.279
39/70 (55.7%)**	0.800	0.200

*For a true CR rate of 38.6% (null value), the probability for a trial success is 2.0% (*type-l error*). **For a true CR rate of 55.7%, the probability for a trial success is 80% (*power*).

These calculation were made using the software R (version 3.6.1) using the RBestT package.

3 Change to protocol specified analyses

As Novartis decided to halt the enrollment in the expansion part in September 2022, the following analyses as per protocol will not be performed due to data limitations:

- The primary analysis of CR rate
- The analysis of Patient-Reported outcome: MDS symptoms and fatigue

4 Appendix - General definitions

Date of first administration of study treatment (sabatolimab or azacitidine or venetoclax)

The date of first administration of any study treatment component (sabatolimab or azacitidine or venetoclax) is defined as the first date when a non-zero dose of the respective study drug is administered and recorded on the study treatment eCRF page.

Date of last administration of study treatment (sabatolimab or azacitidine or venetoclax)

The date of last administration of any study treatment component (sabatolimab or azacitidine or venetoclax) is defined as the last date when a non-zero dose of the respective study drug is administered and recorded on the study treatment eCRF page. So both, first and last date of study drug, are derived separately for each drug which is part of the study treatment.

Date of first administration of study treatment (combination)

The date of first administration of study treatment (or start date of study treatment) is defined as the first date when a non-zero dose of any component of the study treatment (sabatolimab, Azacitidine or venetoclax) is administered.

Date of last administration of study treatment (combination)

The date of last administration of study treatment (or start date of study treatment) is defined as the last date when the last non-zero dose of any last component of the study treatment (sabatolimab, Azacitidine or venetoclax) is administered.

Date of last exposure to study treatment component (sabatolimab or azacitidine or venetoclax)

One planned cycle length is 28 days and the start date of a cycle is defined as the first administration of azacitidine within a cycle. Azacitidine is planned to be administered daily every cycle during 7 days at the beginning of each cycle (between Day 1 to Day 9). Sabatolimab is administered every 4 weeks (Q4W), on Day 8 of each cycle, unless there was a toxicity leading to a dosing interval increase. Venetoclax is planned to be administered once a day from day 1 to day 14 of the 28-day cycle.

The date of last exposure to sabatolimab is therefore calculated as:

• Minimum (last date of administration of sabatolimab + 27 days, date of death, last contact date in case participant is lost to follow-up), as sabatolimab injections are given Q4W.

The date of last exposure to azacitidine is calculated as:

• Minimum (last date of administration of azacitidine + 20 days, date of death, last contact date in case participant is lost to follow-up) as the 7 doses of azacitidine are given in the beginning of each cycle.

The date of last exposure to venetoclax is calculated as:

• Minimum (last date of administration of venetoclax + 14 days, date of death, last contact date in case participant is lost to follow-up) as the 14 doses of venetoclax are given in the beginning of each cycle (in case of regimen change to "one week on, three weeks off" in the last cycle, last date of administration of venetoclax + 21 days will be considered.)

End date of the last cycle initiated

The end date of the last cycle initiated is the maximum date between:

- The planned end date (Day 28) of the last cycle initiated when the last non-zero dose of any last component of the study treatment (sabatolimab or azacitidine or venetoclax) is administered,
- The actual date of the last administration of a non-zero dose of any last component of the study treatment.

The end date of the last cycle initiated (Day 28 or beyond) will be applicable even if this date goes beyond the data cut-off date (i.e., it should not be truncated to the date of data cut-off).

Date of last exposure and duration of exposure to study treatment (combination)

For the calculation of the duration of exposure to study treatment (combination), the date of last exposure to study treatment (combination) will be derived as the minimum date between:

- The latest one of the date of last exposure to any study treatment component (sabatolimab or azacitidine or venetoclax),
- Date of death,
- Last contact date in case participant is lost to follow-up.

The duration of exposure to study treatment (combination) will be calculated as follow: date of last exposure to study treatment (combination) - date of first administration of study treatment (combination) + 1.

Duration from first to last cycle initiated to calculate dose intensity and the relative dose intensity

For the calculation of the dose intensity and relative dose intensity, the duration in days from first to last cycle initiated will be calculated as follow: end date of the last cycle initiated - date of first administration of study treatment (combination) + 1.

Thus, this derivation will be irrespective of date of death or last contact date (i.e., it should not be truncated to the date of death or date of last contact date).

Study day

The study day, describes the day of the event or assessment date, relative to the reference start date (start date of study treatment).

The study day is calculated as follows:

- The date of the event (visit date, onset date of an event, assessment date etc.) reference start date + 1 if event is on or after the reference start date;
- The date of the event (visit date, onset date of an event, assessment date etc.) reference start date if event precedes the reference start date.

The reference start date for safety assessments (e.g. adverse event onset, laboratory or ECG assessment, vital sign measurement etc.) is the start of study treatment. The same reference start date will be used for efficacy (e.g. response assessment, time-to-event endpoints) and patient-reported outcomes (PRO).

The study day will be displayed in the data listings. If an event starts before the reference start date, the study day displayed on the listing will be negative.

Time unit

A year length is defined as 365.25 days. A month length is 30.4375 days (365.25/12). If duration is reported in months, duration in days will be divided by 30.4375. If duration is reported in years, duration in days will be divided by 365.25.

Baseline

For efficacy evaluations and PROs, the last non-missing assessment, including unscheduled assessments on or before the date of start of study treatment is taken as "baseline" value or "baseline" assessment.

For safety evaluations, the last available assessment including unscheduled assessments on or before the date of the start of study treatment is taken as "baseline" assessment. If participants have no value as defined above, the baseline result will be missing.

Windows for multiple assessments

Time windows will be defined for descriptive summary of ECOG and PRO data (EORTC QLQC30, by visit and the longitudinal data analysis. If more than one assessment is available in the same time window, the assessment closest to the planned date will be considered. If two assessments are obtained with the same time difference compared to the scheduled visit day, the assessment obtained prior to the visit will be considered. Data obtained at the end of treatment visit will be classified as other assessment in the corresponding time window. For participants who discontinue treatment for reasons other than progressive disease, withdraw consent or death, EORTC QLQ-C30 5L will continue being collected every 6 months during this follow-up period until disease progression.

Table 4-1	Time windows	for PRO	and ECOG data

Assessment	Target day of assessment	Time Window Definition
Baseline	On or before Study Day 1[a]	≤ Study Day 1
During treatment phase		
Cycle 2 Day 1	Study Day 29	Study Days 2 to 42
Cycle 3 Day 1	Study Day 57	Study Days 43 to 70
Cycle k day 1	Study Day = 28*(k-1) + 1	Study Day

Assessment	Target day of assessment	Time Window Definition
(with k=4, 5, 6, 7, 8 etc)		28*(k-1) +1 -14 to 28*(k-1) +14
		For last cycle of dosing: from 28*(k- 1) +1 -14 to end of treatment visit date +7
		"Note: EOT data will be included if obtained within 7 days of permanent discontinuation of study treatment"
After treatment discontinuati	ion (only EORTC QLQ-C30)
Post treatment follow-up	Every 6 months	For the first time window: [upper bound of the last previous time windows with assessment + 1; PRO assessment date + 84 days] Otherwise: [PRO assessment date -/+ 84 days]
[a] Study Day 1 = randomizatio baseline)	n date will be baseline (exce	pt for which there is no

Last contact date

The last contact date will be used for censoring of participants in the analysis of overall survival.

The last contact date is defined as the latest complete date from the below list on or before the data cut-off date:

	Table 4-2	Last contact date	data sources
--	-----------	-------------------	--------------

Source data	Conditions
Date of start of treatment	Non-missing dose
Last date participant was known to be alive from Survival Follow-up page	Participant status is reported to be alive or unknown
Start/End dates from further antineoplastic therapy	Non-missing medication/procedure term
Start/End dates from drug administration record	Non-missing dose
Response assessment date	Response marked as 'done'
Laboratory/PK collection dates	Sample collection marked as 'done'
Vital signs date	At least one non-missing parameter value
ECOG performance status date	Non-missing performance status
Start/End dates of AE	Non-missing verbatim term

The cut-off date will not be used for last contact date, unless the participant was seen or contacted on that date. No date post cut-off date will be used.

Completely imputed dates (e.g. the analysis cut-off date programmatically imputed to replace the missing end date of a dose record) will not be used to derive the last contact date. Partial date imputation is allowed for event (death)/censoring only if coming from the 'Survival' eCRF.

The last contact date will be derived for participants not known to have died at the analysis cutoff using the last complete date among the following:

5 Reference

